18.4 Missing Date of Investigational Product

Since this is a Phase 1 single-dose study in which the investigational product will be administered on Day 1, missing dates of investigational product are not expected.

18.5 Missing Date Information for Prior or Concomitant Medications

For prior or concomitant medications, including rescue medications, incomplete (i.e., partially missing) start date and/or stop date will be imputed. When the start date and the stop date are both incomplete for a subject, the start date will be imputed first.

18.5.1 Incomplete Start Date

The following rules will be applied to impute the missing numerical fields. If the stop date is complete and the imputed start date is after the stop date, then the start date will be imputed using the stop date.

Note: This is a single-dose study, and thus the use of “first dose” below equates to “dose.”

Missing day and month

- If the year of the incomplete start date is the same as the year of the date of the first dose of investigational product, then the day and month of the date of the first dose of investigational product will be assigned to the missing fields.
- If the year of the incomplete start date is before the year of the date of the first dose of investigational product, then December 31 will be assigned to the missing fields.
- If the year of the incomplete start date is after the year of the date of the first dose of investigational product, then 01 January will be assigned to the missing fields.

Missing month only

- The day will be treated as missing and both month and day will be replaced according to the above procedure.

Missing day only

- If the month and year of the incomplete start date are the same as the month and year of the date of the first dose of investigational product, then the day of the date of the first dose of investigational product will be assigned to the missing day
- If either the year is before the year of the date of the first dose of investigational product or if both years are the same but the month is before the month of the date of the first dose of investigational product, then the last day of the month will be assigned to the missing day
- If either the year is after the year of the date of the first dose of investigational product or if both years are the same but the month is after the month of the date of the first dose of investigational product, then the first day of the month will be assigned to the missing day.

18.5.2 Incomplete Stop Date

The following rules will be applied to impute the missing numerical fields. If the date of the last dose of investigational product is missing, then it will be replaced with the last visit date. If the imputed stop date is before the start date (imputed or non-imputed start date), then the imputed stop date will be equal to the start date.

Missing day and month

- If the year of the incomplete stop date is the same as the year as of the date of the last dose of investigational product, then the day and month of the date of the last dose of investigational product will be assigned to the missing fields
- If the year of the incomplete stop date is before the year of the date of the last dose of investigational product, then 31 December will be assigned to the missing fields

- If the year of the incomplete stop date is after the year of the date of the last dose of investigational product, then 01 January will be assigned to the missing fields.

Missing month only

- The day will be treated as missing and both month and day will be replaced according to the above procedure.

Missing day only

- If the month and year of the incomplete stop date are the same as the month and year of the date of the last dose of investigational product, then the day of the date of the last dose of investigational product will be assigned to the missing day
- If either the year is before the year of the date of the last dose of investigational product or if both years are the same but the month is before the month of the date of the last dose of investigational product, then the last day of the month will be assigned to the missing day
- If either the year is after the year of the last dose of investigational product or if both years are the same but the month is after the month of the date of the last dose of investigational product, then the first day of the month will be assigned to the missing day.

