9. PRIOR AND CONCOMITANT MEDICATIONS

Prior and concomitant medications will be coded using the World Health Organization-Drug Dictionary (WHO-DD) Version September 2017 or higher.

For statistical analysis purposes, prior and concomitant medications are defined as follow (“time” implies date and time):

- **Prior medication:** Any medication with start time **prior to** time of investigational product administration.
- **Concomitant medication:** Any medication with start time **at or after** time of investigational product administration, OR medications with start time **prior to** investigational product administration but continuing at or after investigational product administration. Any medication with a start date after the end of the follow-up period (Day 112/ End of Study Visit) will be considered post-treatment medication and not concomitant medication.

For medications with partial onset times, non-missing date parts will be used to determine if the medication is concomitant or prior medication. If a determination cannot be made using the non-missing date parts as to when the medication occurred relative to investigational product administration then the medication will be classified as concomitant medication. Additional information is provided in [Section 18.5](#).

Both prior and concomitant medication usage will be summarized by therapeutic class and preferred term, and based on the Safety Analysis Set. The summary will include number and percentage of subjects who took the medication. Therapeutic class will be sorted alphabetically, and PT will be sorted within each therapeutic class in descending frequency in the table Total column (i.e., the Total column will be sorted in descending order after sorting by therapeutic class and PT). Medications can be counted both as prior and concomitant medications. Multiple medication usage by a subject in the same PT will be counted only once for that PT. All prior and concomitant medications will be listed, and the listings will be based on the Safety Analysis Set.

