18.6 Missing Date Information for Adverse Events

For AEs, incomplete (i.e., partially missing) start dates will be imputed and will follow the same rules as in [Section 18.5.1](#). Incomplete stop dates will not be imputed.

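### SAP 18.5.1 checks an imputed start date only against a complete stop date, so in one date pattern a medication or AE recorded as ending in a month before dosing is given a start on the dosing day

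*SAP*

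**What the plan says.** SAP 18.5 fixes the order: "When the start date and the stop date are both incomplete for a subject, the start date will be imputed first".

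SAP 18.5.1 gives the start rules. If the month is missing (the day is then treated as missing too) and the year is the dosing year, "then the day and month of the date of the first dose of investigational product will be assigned to the missing fields". The guard against a start later than the stop is conditional: "If the stop date is complete and the imputed start date is after the stop date", the stop serves to impute the start. Nothing is said about a stop date that is only partly known.

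SAP 18.5.2 places a stop date that lacks only its day, in a month before the dosing month, on the last day of that month. It then adds: "If the imputed stop date is before the start date (imputed or non-imputed start date), then the imputed stop date will be equal"; the target is that start.

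SAP 18.6 deals with AEs: "start dates will be imputed and will follow the same rules as in" Section 18.5.1, and incomplete AE stop dates are left unimputed.

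SAP 9 has its own rule for medications with a partial onset: "non-missing date parts will be used to determine if the medication is concomitant or prior medication". Concomitant is the default only when those parts cannot settle the matter. The section then points to 18.5 for additional information.

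**The concern.** The guard in 18.5.1 shows that the authors did not want a start imputed past a known stop. It covers complete stop dates and omits a stop date whose month and year are known. When that month is before dosing, the imputation contradicts what was recorded.

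For a medication, the result is a start and stop on the dosing day for a drug recorded as finished. On those dates it would leave the prior-medication table (14.1.4.4.1), because a prior drug must start before dosing, and enter the concomitant table (14.1.4.5.1). For an AE, the onset is placed on the dosing day while the recorded stop stays in an earlier month. That sequence is impossible, yet it meets the TEAE definition in SAP 11.1. At stake are a few entries in safety and background tables.

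**Working it through.** The plan states no figure on this point, so the check traces the written rules on example dates.

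**Inputs.** Order of imputation: SAP 18.5. Start rules and guard: 18.5.1. Stop rules and conflict rule: 18.5.2. AE rule: 18.6. The dosing date of 15 March 2018 is my assumption; the Protocol synopsis gives only 2018 as the planned period. An imputed date has no clock time, so I count a date equal to the dosing date as at or after dosing.

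| Recorded start | Recorded stop | Imputed start | Imputed stop | Reaches dosing day? |
|---|---|---|---|---|
| 2018 | Feb 2018 | 15 Mar 2018 | 28 Feb, then moved to 15 Mar 2018 | Yes |
| 2018 | 20 Feb 2018 | 20 Feb 2018 (from stop) | 20 Feb 2018 (recorded) | No |
| Jan 2018 | Feb 2018 | 31 Jan 2018 | 28 Feb 2018 | No |
| Feb 2018 | Feb 2018 | 28 Feb 2018 | 28 Feb 2018 | No |
| 5 Feb 2018 | Feb 2018 | 5 Feb 2018 (recorded) | 28 Feb 2018 | No |
| 2017 | Feb 2018 | 31 Dec 2017 | 28 Feb 2018 | No |
| 2017 | Nov 2017 | 31 Dec 2017 | 30 Nov, then moved to 31 Dec 2017 | No, but the recorded stop month is overwritten |

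Rows 1 and 2 differ only in whether the stop day is known, and they fall on opposite sides of dosing. Rows 3 and 4 are safe because of the rule for a start with a known month: "month is before the month of the date of the first dose of investigational product, then the last day of the month will be assigned".

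**How narrow the pattern is.** Take dosing on the 15th of each month of 2018, spells ending 1 to 12 months earlier, and lengths of 0 to 12 months: 12 × 12 × 13 = 1,872 spells. Of these, 286 start in the dosing year (the sum of M(M−1)/2 over dosing months M = 1 to 12) and 1,586 start earlier. Crossing the start (complete, day missing, month missing) with the stop (complete, day missing) and the start year (dosing year, earlier) gives 3 × 2 × 2 = 12 patterns. Start month missing, in the dosing year, with the stop day missing: 286 of 286 reach the dosing day. The other 11 patterns: none. These counts describe the rule and say nothing about how often such records will arise. With January dosing the pattern cannot occur, because every earlier month lies in the previous year.

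**Medications (row 1), read against SAP 9.**
- If the imputed dates govern, the drug is concomitant.
- If only the onset parts count, the year alone cannot decide and the default is concomitant.
- If the recorded stop month counts, the drug is prior, and the dates from 18.5 contradict that class.

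The SAP does not say which applies. None of the three leaves the record, the imputed dates and the classification in agreement.

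**AEs (row 1).** Under 18.6 and 18.5.1 the onset becomes 15 March 2018 and the recorded stop remains February 2018. SAP 9's date-parts rule covers medications only, so nothing corrects this and the event counts as a TEAE.

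**Could such records be collected?** Screening lasts at most 28 days (Protocol 7.1.1), and medication history goes back 30 days before it (Protocol 7.2.2.1): up to 28 + 30 = 58 days before dosing. A drug that ended in February 2018 ended 15 to 42 days before 15 March. AEs are collected from consent; 28 days before 15 March is 15 February, so an AE from 15 to 28 February fits.

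**Size.** SAP 9 and 11.1 base these summaries on the Safety Analysis Set, meaning all dosed subjects. With the planned 16 per group, one subject is 1/16 = 6.25%, or 6.3 percentage points. This is a maximum, because the subject may already be counted for another drug or event.

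**After the fix.** In row 1 the start is capped at 28 February 2018. The drug is prior only and the AE is not treatment-emergent. The affected pattern goes from 286/286 to 0/286, because the last day of the recorded stop month always precedes the dosing month.

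**The case against.** The strongest reply is that little will come of this. It needs an unknown start month together with a known stop month. Data queries (Protocol 9.2) should remove some partial dates. An affected AE must begin and end within at most 28 days before dosing and end in an earlier calendar month. Defaults towards concomitant, severe and related look deliberately cautious. All of this stands as to frequency. It does not defend the rule: caution suits unknown dates, and here the recorded month already settles the question.

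Five stronger readings are tempting and are not supported:

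- *Any record ending in a month before dosing is moved.* Only the one pattern is; a complete stop or a known start month is handled correctly.
- *The drug is certainly counted as concomitant.* SAP 9, not 18.5, classifies medications, and its default turns on when the drug was taken relative to dosing. A recorded stop month can answer that. What the text supports is unclear precedence.
- *The conflict rule in 18.5.2 causes the AE problem.* It cannot, because AE stop dates are not imputed. The route is 18.6 with 18.5.1.
- *A false breach of the 14-day medication-free window appears.* Moving a 2017 stop to 31 December 2017 could suggest this for a January 2018 dose. But eligibility is confirmed before enrolment (Protocol 4.1), deviations are only listed under sponsor procedures (SAP 6), and no document derives them from imputed dates. The drug also stays prior.
- *The change is 1/12 (8.3 points).* Twelve is the expected number of completers per group. The tables use dosed subjects, so dropouts stay in the denominator.

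SAP 18.7 and 18.8 would make such an AE severe and related only if those fields were also missing and those rules used the imputed start date, which the SAP does not state.

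**Conclusion.** The point holds in a narrow form. When the start lacks its month in the dosing year and the stop lacks only its day in an earlier month of that year, SAP 18.5.1 puts the start on the dosing date. For medications, 18.5.2 then overrides the recorded stop month, and precedence between SAP 9 and the imputed dates is undefined. For AEs, a pre-dose event is counted as treatment-emergent.

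The effect is at most 6.3 percentage points per affected subject in a group's rate, assuming 16 dosed subjects per group and comparison at date level. Affected records should be few, and neither the primary PK analysis nor any other PK endpoint is touched. This is a minor correction, worth making because a program written to the text would replace recorded information in safety tables.

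**What to change.** 1. In SAP 18.5.1, replace the complete-stop condition: if the imputed start is after the latest date allowed by the stop date, whether complete or partial (last day of the recorded month or year), set the start to that latest date. State in 18.6 that this also applies to AEs and uses the recorded parts of an incomplete AE stop date, even though that stop date is not itself imputed.
2. In SAP 18.5.2, add that an imputed stop date is never moved outside its recorded month or year. This also corrects the year-end case in the last row of the table.
3. In SAP 9, state that the recorded date parts, including those of the stop date, take precedence over imputed dates in classifying a medication as prior or concomitant.

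Records that cannot be decided keep their cautious default: with only 2018 recorded for both dates, the cap is 31 December 2018 and the start stays on the dosing date. The cost is these sentences and a small change to the imputation program. Design, endpoints and data collection are unchanged.

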18.6 Missing Date Information for Adverse Events

For AEs, incomplete (i.e., partially missing) start dates will be imputed and will follow the same rules as in [Section 18.5.1](#). Incomplete stop dates will not be imputed.

18.7 Missing Severity Assessment for Adverse Events

If severity is missing for an AE starting prior to the date of the first dose of investigational product, then a severity of “Mild” will be assigned. If the severity is missing for an AE starting on or after the date of the first dose of investigational product, then a severity of “Severe” will be assigned. The imputed values for severity assessment will be used for incidence summaries, while the actual values will be used in data listings.

18.8 Missing Relationship to Investigation Product for Adverse Events

If the relationship to investigational product is missing for an AE starting on or after the date of the first dose of investigational product, a causality of “Related” will be assigned. The imputed values for relationship to the investigational product will be used for incidence summaries, while the actual values will be presented in data listings.

18.9 Character Values of Clinical Laboratory Variables

The actual values of clinical laboratory variables as reported in the database will be presented in data listings. No coded values (e.g., when a character string is reported for a numerical variable) are necessary.

